## **9. STUDY EVALUATIONS**

### **9.1. Study Procedures**

#### **9.1.1. Overview**

Evaluation of the safety/tolerability of the vaccine regimens will include physical assessment by study-site personnel, and subject reports on signs and symptoms following vaccinations. Additional visits may be required if in the investigator's opinion, further clinical or laboratory evaluation is needed.

Each Cohort 0 subject, and each Cohort 1 subject's parents/legal guardian or caregiver will be provided with a thermometer, ruler, and subject diary to measure and record body temperature and solicited local (at injection site) and systemic events.

The diary includes instructions how to capture the data and grading scales to assess severity of the symptoms. Study staff are responsible for providing appropriate training for diary completion to avoid missing or incorrect data. The diary will be reviewed by the study personnel at visits indicated on the [Time and Events Schedule](#).

For Cohort 0, at each visit/telephone call, each adult subject should be informed that, in the event of developing a combination of symptoms of respiratory infection (persistent [ $>48$  hours] clinical symptoms of rhinitis [sneezing or runny nose or congestion] and persistence [ $>24$  hours] of one or more of the following: cough, abnormal breathing, fever, lethargy or decreased appetite), they should contact the site as soon as possible.

For Cohort 1 only, at each visit/telephone call, each subject's parents/legal guardian or caregiver should be informed that, in the event that their child develops a combination of symptoms of respiratory infection (persistent [ $>48$  hours] clinical symptoms of rhinitis [sneezing or runny nose or congestion] and persistence [ $>24$  hours] of one or more of the following: cough, abnormal breathing, fever, lethargy or decreased appetite), they should contact the site as soon as possible.

The [Time and Events Schedule](#) summarizes the frequency and timing of safety and immunogenicity measurements applicable to this study.

The total blood volume to be collected from each subject in Cohort 0 over approximately 34 weeks from screening will be approximately 295 mL.

The total blood volume to be collected from each subject in Cohort 1 over approximately 36 weeks from screening will be approximately 14.5 mL.

### **9.1.2. Visit Windows**

For the following visits, windows will be allowed as indicated:

- Second vaccination:  $\pm 3$  days (both cohorts)
- 3 days post-vaccination safety only visit:  $\pm 1$  day
- 7 days post-vaccination safety only visit:  $\pm 2$  days
- 28 days post-final vaccination safety and immunogenicity visit:  $\pm 3$  days
- 6 months post-final vaccination safety and immunogenicity visit:  $\pm 14$  days
- 1 year post-first vaccination safety follow-up telephone call:  $\pm 14$  days

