- For those subjects who are unable to continue participation in the study up to Visit 9, but for whom consent is not withdrawn, an exit visit will be conducted as soon as possible
- On Days 3 and 31, a telephone call will *additionally* be made to sentinel subjects in Cohort 0 to collect safety information
- On Days 3 and 31, a telephone call will *additionally* be made to parent(s)/legal guardian(s) of sentinel subjects in Cohort 1 to collect safety information
- If any subject in Cohort 0, or any of the first 12 subjects in Cohort 1 come in earlier than Day 8 for Visit 4 (allowed window is ±2 days), a subsequent phone call will be made at the end of the diary period to collect diary card information recorded between the actual visit and the end of the diary period on Day 8
- Signing of the ICF should be done before any study-related activity
- Systolic and diastolic blood pressure, respiratory rate, heart rate, body temperature
- Respiratory rate, heart rate, body temperature
- For women of childbearing potential only

- l. 0.5 mL of blood for serostatus assessment can be collected at screening by venous blood sample or fingerstick, at the discretion of the investigator. If 0.5 mL is collected at screening, baseline blood draw for immunogenicity should be on Day 1.
- m. Note: RSV-seropositive toddlers may be recruited if RSV seropositivity was assessed via RSV EIA or virus neutralization assay in a different study of the sponsor.
- n. Cohort 0: to include exclusion criteria 1, 4, 8, 9, 10, 11, 15, 16 and 17
- o. Cohort 1: to include exclusion criteria 21, 22, 25, 26, 28, and 32
- p. Blood for cellular immunity will also provide plasma for humoral assessments
- q. Investigator must check for acute illness or body temperature  $\geq 38.0$  °C at the time of vaccination. If before the first vaccination, the subject may be enrolled at a later date if within the screening window (otherwise, rescreening is required), or be withdrawn at the discretion of the investigator and after consultation with the sponsor. If before the second vaccination, the subject may be vaccinated up to, and no later than 10 days after the scheduled vaccination, or be withdrawn at the discretion of the investigator and after consultation with the sponsor. In the event of an ongoing AE or other situation precluding subject vaccination within 10 days, subjects may be vaccinated beyond the 10-day window at the discretion of the sponsor.

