### **2.1.2. Endpoints**

#### **Primary Endpoints – Safety and Tolerability**

- Solicited local and systemic AEs for 7 days after each vaccination.
- Unsolicited AEs for 28 days after each vaccination (ie, from informed consent form [ICF] signature through the following 28 days post-first vaccination, and for subsequent vaccinations from time of vaccination through the following 28 days).
- SAEs from ICF signature to the end of the study.

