### Safety Follow-up

Parent(s)/legal guardian(s) of subjects in Cohort 1 will be contacted by telephone (or clinic visit) through 1 year after the first dose (including during the active phase and safety follow-up phase: every 30 days  $\pm$  7 days outside the RSV season, but every 14 days  $\pm$  3 days in season). During each 28-day post-vaccination period, calls will remind parents/legal guardians to contact the site in the event their child develops an RTI. During the RSV season, but outside the 28-day post-vaccination period, calls will remind parents/legal guardians to contact the site in the event their child develops a combination of symptoms of respiratory infection (persistent [ $>48$  hours] clinical symptoms of rhinitis [sneezing or runny nose or congestion] and persistence [ $>24$  hours] of one or more of the following: cough, abnormal breathing, fever, lethargy or decreased

appetite). These calls will also check for any SAEs and associated concomitant medications since the previous visit or telephone contact.

### 3.2. RTI – Procedures Specific to Cohort 1

Monitoring of RTIs will take place during each 28-day post-vaccination period, and additionally during the RSV season after the first dose (even if it falls outside of the 28-day post-vaccination period). Monitoring for MA-RTIs and severe LRTIs will take place during the whole study period.

During each 28-day post-vaccination period, all RTIs will be reported, nasal turbinate samples will be collected as soon as possible after the onset of respiratory symptoms, and signs and symptoms will be recorded by the attending health care professional using the RTI Symptoms Form.

If, during the RSV season, but outside the 28-day post-vaccination period, a subject shows persistent (>48 hours) clinical symptoms of rhinitis (sneezing or runny nose or congestion) and persistence (>24 hours) of one or more of the following: cough, abnormal breathing, fever, lethargy or decreased appetite, the study site should be notified. Nasal turbinate samples will be collected as soon as possible after the onset of these combined respiratory symptomsa. When nasal turbinate samples are collected, the attending health care professional will record signs and symptoms of the RTI using the RTI Symptoms Form.

Nasal turbinate samples will not be collected if less than 7 days after the previous sample collection.

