Unsolicited AEs will be recorded on the AE page of the eCRF from the signing of the ICF until 28 days after the first vaccination and from the second vaccination through the following 28 days, together with information about any concomitant medications. SAEs will be collected from ICF signature through 1 year after the first dose.

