#### **9.1.3.2.4. Final Visit – 6 Months After the Second Vaccination**

**Visit 8** at 6 months after the second vaccination will include an abbreviated physical examination (at the discretion of the investigator), vital signs measurement (at the discretion of the investigator), recording of any SAEs and associated concomitant medications. Blood samples will be collected for immunogenicity assessments.

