**Visit 5: Day 29/Vaccination 2**

After verification of selected eligibility criteria,c abbreviated physical examination (at the discretion of the investigator) and measurement of vital signs, body height and weight will be performed for all subjects pre-vaccination. Pre-dose samples for immunogenicity assessments will be collected. Before the second vaccination, the investigator must check for any symptoms of an acute illness. In such a situation, the subject may be vaccinated up to, and no later than 10 days after the scheduled vaccination, or be withdrawn at the discretion of the investigator and after consultation with the sponsor. In the event of an ongoing AE or other situation precluding

---

a Exclusion criterion 21, 22, 25, 26, 28, and 32.

b If within the screening window. Otherwise, rescreening is required.

c Exclusion criterion 21, 22, 25, 26, 28 and 32.

subject vaccination within 10 days, subjects may be vaccinated beyond the 10-day window at the discretion of the sponsor.

Administration of second dose of study vaccine.

Subjects will be closely observed for a minimum of 30 minutes post-vaccination, or a minimum of 60 minutes post-vaccination according to local approvals, to monitor for the development of any acute reactions, or longer if deemed necessary by the investigator. Any unsolicited, solicited local or systemic AEs and vital signs will be documented in the eCRF by study-site personnel following this observation period.

A subject diary, thermometer, and ruler will be provided to measure and record body temperature and solicited local and systemic AEs for 7 days post-vaccination.

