## **11.8. Planned Analyses**

The following analyses will be performed:

- **Cohort 0:** primary analysis will be performed when all subjects have reached Day 57 (28 days post-Dose 2) or discontinued earlier. All available safety and immunogenicity data gathered so far will be included in the analysis; unblinded at the group level.
- **Cohort 1:** interim analysis will be performed when at least 24 subjects have reached Day 29 (28 days post-Dose 1) or discontinued earlier. All available safety and immunogenicity data gathered so far will be included in the analysis; unblinded at the group level.
- **Cohort 1:** primary analysis will be performed when all subjects have reached Day 57 (28 days post-Dose 2) or discontinued earlier. All available safety and immunogenicity data gathered so far will be included in the analysis; unblinded at the group level.
- **Final analysis of both cohorts;** at the end of the study, 1 year after the first dose; unblinded

Additional interim analyses (blinded or unblinded at the group level) may be performed during the study for the purpose of informing future vaccine-related decisions in a timely manner, or upon health authority request. The results will not influence the conduct of the study in terms of

early termination or later safety or immunogenicity endpoint assessments, and will only be available to a selected group of sponsor personnel, excluding sponsor personnel involved in data collection or data management.

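### An early 28-day visit after dose 2 leaves up to 3 of the 28 days of the unsolicited-AE primary endpoint without a scheduled enquiry for non-serious events

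*Protocol*

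**What the plan says.** Protocol 2.1.2 lists among the primary endpoints "Unsolicited AEs for 28 days after each vaccination". Protocol 9.1.3.1 defines the second recording period by time since dose: "from the second vaccination through the following 28 days". The same rule is given for toddlers in 9.1.4.1.

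Protocol 9.1.2 gives the "28 days post-final vaccination safety and immunogenicity visit" a window of ±3 days. Sections 9.1.3.2.3 (Visit 7, adults) and 9.1.4.2.3 (Visit 8, toddlers) make this the last scheduled visit at which unsolicited AEs of any kind are recorded.

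Later contacts ask for less:
- **Cohort 0.** The six-month visit provides for "recording of any SAEs and associated concomitant medications" (9.1.3.2.4). The one-year call is also limited to serious events (9.1.3.3).
- **Cohort 1.** Of the surveillance calls, protocol 3.1 says "These calls will also check for any SAEs and associated concomitant medications". Section 9.1.4.3 adds medically attended respiratory infections, severe lower respiratory infections and any medical care sought. Visit 9 records serious events and respiratory infections. Under 9.2.3.1, all toddler respiratory infections in the 28-day period also go on the AE page.

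In the analysis, SAP Table 2 ends the post-dose 2 period at the later of 28 days and the four-week visit, cut short only by early discontinuation or an interim cut-off. SAP 5.1.4 treats a subject with no reported event as event-free.

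**The concern.** The endpoint and the SAP both run to day 28, but the visit that collects the data may compliantly take place up to three days sooner. For an adult seen on day 25, no later scheduled contact asks about a non-serious event that starts on days 26 to 28. For a toddler, the same is true of non-serious, non-respiratory events.

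The SAP rules make this matter. A late visit lengthens the analysis period, but an early visit does not shorten it. The days not asked about stay in the period and are scored as free of events. The error can only go one way, toward fewer AEs. Safety is the only primary objective, and the active groups are small (8 adults, 24 toddlers).

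**Working it through.** **1. Earliest compliant visit.** The nominal timing is Day 57 − Day 29 = 28 days after dose 2, which agrees with the plan. With the ±3-day window counted from dose 2, as 9.1.2 does, the visit falls between 28 − 3 = 25 and 28 + 3 = 31 days after dose 2. The largest gap is 28 − 25 = 3 days, or 3/28 = 10.7% of the period. It is zero for anyone seen on day 28 or later.

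**2. The plan's own detection table.** Protocol 11.2 gives the chance of at least one AE in N subjects at true rate p. The formula is 1 − (1 − p)^N, and all 28 printed cells reproduce. For N = 24 and p = 5%, 1 − 0.95^24 = 70.8% (printed as 71%).

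**3. Effect of a shortened enquiry.** Assume a constant hazard over 28 days, which the documents do not state. The rate observed over d days is then p_d = 1 − (1 − p)^(d/28). With d = 25 and p = 5%, p_25 = 1 − 0.95^(25/28) = 4.48%.

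If every subject is seen on day 25 and nothing is captured afterwards, the chance of at least one AE is 1 − (1 − p)^(25N/28):

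| Active group | 28-day rate | 28 days covered | 25 days covered | Loss (points) |
|---|---|---|---|---|
| N = 24 toddlers | 5% | 70.8% | 66.7% | 4.1 |
| N = 24 toddlers | 10% | 92.0% | 89.5% | 2.5 |
| N = 8 adults | 5% | 33.7% | 30.7% | 3.0 |

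**4. Partial early attendance.** If only 12 of the 24 toddlers were seen on day 25, the exponent is 12 + 12 × 25/28 = 22.71. At 5% the chance is 1 − 0.95^22.71 = 68.8%, a loss of 2.0 points.

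**5. Protocol 12.3.1.** This section qualifies the 28 days with a parenthesis that takes in the relevant visit window. If that lets an early visit close the period, it contradicts SAP Table 2, which never closes before day 28 for a subject still in the study. If it only extends the period for a late visit, the gap remains. The text does not say which is meant.

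**The case against.** The strongest reply is that collection is defined by time since dose, not by visit. The schedules show unsolicited AE recording as continuous, subjects carry a card with a 24-hour investigator number, and AE enquiry is meant to be open-ended (protocol 12). A non-serious event on day 27 can therefore still be reported and would have to be recorded. This stands. A reader might infer that the 28-day follow-up is not delivered at all. The documents support only that no scheduled contact guarantees the last days for subjects seen early.

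A reader might also infer that every later contact is confined to serious events. That is right for adults but wrong for toddlers, whose later contacts also cover respiratory infections and medical care sought.

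A third tempting reading counts Day 57 ± 3 from Day 1. Dose 2 on Day 32 would then leave 54 − 32 = 22 days. Dose 2 may also be deferred ("the subject may be vaccinated up to, and no later than 10 days after the scheduled vaccination"; and, under the schedule footnote, "subjects may be vaccinated beyond the 10-day window at the discretion of the sponsor"). With dose 2 on Day 39, the visit would fall 15 to 21 days after it. The documents do not support this reading. Section 9.1.2, the visit-timing row of both schedules, the visit descriptions and SAP Table 2 all count from dose 2. The analysis trigger in 11.8 ("primary analysis will be performed when all subjects have reached Day 57 (28 days post-Dose 2) or discontinued earlier") itself equates Day 57 with 28 days after dose 2. It also loses no data permanently, because a final analysis follows.

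The protocol does arrange a telephone call to complete the diary after an early seven-day visit, but this is a limited precedent. It applies only to Visit 4 and, in Cohort 1, only to the first 12 toddlers.

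Finally, the 11.2 table is generic and is not tied to unsolicited AEs after dose 2. It serves here only as a yardstick.

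**Conclusion.** The point holds in a limited form. For subjects seen before day 28 after dose 2, up to 3 of the 28 days (10.7%) have no scheduled enquiry for non-serious AEs (non-respiratory ones in Cohort 1). The SAP nonetheless analyses those days as observed and event-free. The possible bias is downward and small. It is 4.1 percentage points of detection probability at a 5% rate with N = 24, and that figure requires all 24 to attend on day 25, a constant hazard and no spontaneous reporting. The loss is smaller if few attend early or if AEs cluster soon after dosing. The documents give no data on early attendance. The safety analysis is descriptive with no hypothesis test, so no formal conclusion is at stake. The change is worth making because it protects a primary endpoint at very little cost.

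**What to change.** 1. In protocol 9.1.3.2.3, 9.1.4.2.3 and both schedules, state that if Visit 7 (Cohort 0) or Visit 8 (Cohort 1) takes place before 28 full days after the actual dose 2, unsolicited AEs with onset through day 28 are completed by telephone. In Cohort 1, use the next scheduled surveillance call. In Cohort 0, make one brief call.
2. Align protocol 12.3.1 with SAP Table 2, so that both say whether the visit window can only lengthen the 28-day period.
3. As a clarification only, state that Day 57 in the schedules and in the primary-analysis trigger (protocol 11.8, SAP 1) means 28 days after the actual dose 2.

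The cost is wording, one more question on an existing toddler call, and at most one short call per early-attending adult (12 adults in all). No visit or sample is added. Outside the RSV season, toddler calls can be up to 30 + 7 = 37 days apart, so for the last toddlers the completed information may reach only the final analysis.

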### **9.1.3. Screening and Study Visits – Cohort 0 (Adults)**

#### **9.1.3.1. Screening Phase: Days –28 to 1**

Only healthy subjects without acute illness or fever and complying with the inclusion and exclusion criteria specified in Section 4.1.1 and Section 4.2.1, respectively, will be included into the study. The investigator will provide detailed information on the study to the subjects and will obtain written informed consent prior to each subject's participation in the study. All the procedures described in the [Time and Events Schedule](#) will only take place after written informed consent has been obtained.

The following evaluations will be performed to determine eligibility requirements as specified in the inclusion and exclusion criteria:

- Physical examination including vital signs measurement (systolic and diastolic blood pressure, respiratory rate, heart rate and body temperature) and height and weight
- Demographic information
- Medical history
- Review of pre-study medications
- Review of inclusion/exclusion criteria
- Serology testing (HIV type 1 or type 2, hepatitis B, hepatitis C)

- Blood sampling for hematology and biochemistry laboratory testing
- Women of childbearing potential: serum  $\beta$ -hCG pregnancy testing

General eligibility for this clinical study will be dependent on results of laboratory tests and the medical assessment. Study subjects who qualify for inclusion based on the medical history, physical examination, and laboratory results will be contacted and scheduled for enrollment and first vaccination (Visit 2) within 28 days. If necessary, the screening visit may be split into several visits.

Subjects with laboratory values not meeting eligibility criteria at the screening visit may have one repeat testing at the discretion of the investigator if the abnormality is not clinically significant and may be a testing aberrancy. Enrollment of a subject with laboratory values representing toxicity Grades 1 or 2 is allowed if the investigator considers the values not to be clinically significant and reasonable for the population under study. Details on toxicity grade assessment are provided in Section 9.2.3.2.

After laboratory data, medical history and physical examination data have been reviewed for completeness and adherence to inclusion and exclusion criteria, the subject can be deemed eligible for the study.

Unsolicited AEs will be recorded on the AE page of the eCRF from the signing of the ICF until 28 days after the first vaccination and from the second vaccination through the following 28 days, together with information about any concomitant medications. SAEs will be collected from ICF signature through 1 year after the first dose.

### **9.1.3.2. Active Phase – Day 1 to Day 211**

#### **9.1.3.2.1. Vaccination (Days 1 and 29)**

##### **Visit 2: Day 1/Day of Randomization/Vaccination 1**

After re-check of inclusion and exclusion criteriaa, abbreviated physical examination (at the discretion of the investigator) and measurement of vital signs, eligible subjects will be randomized as described in Section 5. If medical status and/or physical examination suggest significant changes have occurred since screening, the laboratory tests will be repeated and the Day 1 visit re-scheduled, or the subject excluded from the study if he/she fails to meet the inclusion and exclusion criteria. Pre-dose samples for baseline immunogenicity assessments as well as pre-dose samples for safety laboratory testing (hematology and biochemistry) and a nasal turbinate sample for immunogenicity assessment will be collected. All women must have a negative urine pregnancy test pre-dose. Before the first vaccination, the investigator must check for any symptoms of an acute illness or body temperature  $\geq 38.0$  °C. In such a situation, the

---

a To include exclusion criteria 1, 4, 8, 9, 10, 11, 15, 16 and 17.

subject may be enrolled at a later datea, or be withdrawn at the discretion of the investigator and after consultation with the sponsor.

Administration of first dose of study vaccine.

Subjects will be closely observed for a minimum of 30 minutes post-vaccination, or a minimum of 60 minutes post-vaccination according to local approvals, to monitor for the development of any acute reactions, or longer if deemed necessary by the investigator. Any unsolicited, solicited local or systemic AEs and vital signs will be documented in the eCRF by study-site personnel following this observation period.

Subjects will be provided with a subject diary, thermometer, and ruler to measure and record body temperature, solicited local and systemic AEs for 7 days post-vaccination.

